### Financial Disclosure

Investigators and sub-Investigators will provide the Sponsor with sufficient, accurate financial information as requested to allow the Sponsor to submit complete and accurate financial certification or disclosure statements to the appropriate regulatory authorities. Investigators are

responsible for providing information on financial interests during the course of the study and for 1 year after completion of the study.

### **Insurance**

Sponsor will provide insurance in accordance with local guidelines and requirements as a minimum for the subjects in this study. The terms of the insurance will be kept in the study files.

### **Informed Consent Process**

- The Investigator or his/her representative will explain the nature of the study to the subject or his/her legally authorized representative and answer all questions regarding the study.
- Subjects must be informed that their participation is voluntary. Subjects or their legally authorized representative will be required to sign a statement of informed consent that meets the requirements of 21 CFR 50, local regulations, ICH guidelines, Health Insurance Portability and Accountability Act (HIPAA) requirements, where applicable, and the IRB/IEC or study center.
- The medical record must include a statement that written informed consent was obtained before the subject was entered in the study and the date the written consent was obtained. The authorized person obtaining the informed consent must also sign the ICF.
- Subjects must be re-consented to the most current version of the ICF(s) during their participation in the study.
- A copy of the ICF(s) must be provided to the subject or the subject's legally authorized representative.
- A subject who is rescreened is not required to sign another ICF if the rescreening occurs within 30 days from the previous ICF signature date.

### **Data Protection**

- Subjects will be assigned a unique identifier by the Sponsor. Any subject records or datasets that are transferred to the Sponsor will contain the identifier only; subject names or any information which would make the subject identifiable will not be transferred.
- The subject must be informed that his/her personal study-related data will be used by the Sponsor in accordance with local data protection law. The level of disclosure must also be explained to the subject.
- The subject must be informed that his/her medical records may be examined by Clinical Quality Assurance auditors or other authorized personnel appointed by the Sponsor, by appropriate IRB/IEC members, and by inspectors from regulatory authorities.

[Redacted]

[Redacted]

[Redacted]	[Redacted]
[Redacted]	[Redacted]
[Redacted]	[Redacted]
[Redacted]	[Redacted]
[Redacted]	[Redacted]
[Redacted]	[Redacted]
[Redacted]	[Redacted]
[Redacted]	[Redacted]
[Redacted]	[Redacted]
[Redacted]	[Redacted]
[Redacted]	[Redacted]
[Redacted]	[Redacted]
[Redacted]	[Redacted]
[Redacted]	[Redacted]

[Redacted]

[Redacted]

[Redacted]

[Redacted]

[Redacted]

[Redacted]

Quality Control and Quality Assurance

[Redacted]

[REDACTED] Quality control will be applied to each stage of data handling.

The following steps will be taken to ensure the accuracy, consistency, completeness, and reliability of the data:

- Central laboratories for clinical laboratory parameters.
- Study center Initiation visit.
- Early study center visits post-enrollment.
- Routine study center monitoring.
- Ongoing study center communication and training.
- Data management quality control checks.
- Continuous data acquisition and cleaning.
- Internal review of data.
- Quality control check of the final clinical study report (CSR).

In addition, Sponsor [REDACTED] may conduct periodic audits of the study processes, including, but not limited to study center, central laboratories, vendors, clinical database, and final CSR. When audits are conducted, access must be authorized for all study-related documents including medical history and concomitant medication documentation to authorized Sponsor's representatives and regulatory authorities.

### Monitoring

Sponsor has engaged the services of a contract research organization, [REDACTED] to perform all monitoring functions within this clinical study. [REDACTED] monitors will work in accordance with [REDACTED] SOPs. The monitor will establish and maintain regular contact between the Investigator and Sponsor.

The monitor will evaluate the competence of the study center, informing Sponsor about any problems relating to facilities, technical equipment, or medical staff. During the study, the monitor will check that written informed consent has been obtained from all subjects correctly and that data are recorded correctly and completely. The monitor is also entitled to compare entries in the eCRFs with corresponding source data and to inform the Investigator of any errors or omissions. The monitor will also assess and control adherence to the protocol and ICH/GCP guidelines at the study center. The monitor will arrange for the supply of study treatment, ensure proper study treatment dispensing/accountability, and appropriate storage conditions are maintained.

Monitoring visits will be conducted according to all applicable regulatory requirements and standards. Regular monitoring visits will be made to each center while subjects are enrolled in the study.

During monitoring visits, all entries in the eCRFs will be compared with the original source documents (source data verification). For the following and all other items, this check will be 100%:

- Subject identification number.
- Subject consent obtained.
- Subject eligibility criteria (inclusion and exclusion criteria).
- Efficacy variables (not directly entered into PRO).
- Safety variables.
- Medical record of AE.

### **Quality Management**

A system should be implemented to manage quality throughout all stages of the study process with the focus on study activities essential to ensuring human subject protection and the reliability of study results. The methods used to assure and control the quality of the clinical study should be proportionate to the risks inherent in the trial and the importance of the information collected. All aspects of the study should be operationally feasible and should avoid unnecessary complexity, procedures, and data collection.

During protocol development, processes and data that are critical to ensure human subject protection and the reliability of trial results should be identified. Risks should be considered at both the system level (eg, standard operating procedures, computerized systems, personnel) and clinical trial level (eg, trial design, data collection, informed consent process). The approach used to reduce risk to an acceptable level should be proportionate to the significance of the risk. Predefined quality tolerance limits should be established, taking into consideration the medical and statistical characteristics of the variables as well as the statistical design of the trial, to identify systematic issues that can impact subject safety or reliability of trial results. Detection of deviations from the predefined quality tolerance limits should trigger an evaluation to determine if action is needed.

Quality management activities should be documented and communicated to those who are involved in or affected by such activities, to facilitate risk review and continual improvement during clinical trial execution.

### **Data Management/Coding**

Electronic data capture will be used for this study, meaning that all eCRF data will be entered in electronic forms at the study centers. Data collection will be completed by authorized study center staff designated by the Investigator. Appropriate training and security measures will be

completed with the Investigator and all designated study center staff prior to the study being initiated and any data being entered into the system for any study subjects.

All data must be entered in English. The eCRFs should always reflect the latest observations on the subjects participating in the study. Therefore, the eCRFs are to be completed as soon as possible during or after the subject's visit. To avoid inter-observer variability, every effort should be made to ensure that the same individual who made the initial Baseline determinations completes all efficacy and safety evaluations. The Investigator must verify that all data entries in the eCRFs are accurate and correct. If some assessments are not done, or if certain information is not available or not applicable or unknown, the Investigator should indicate this in the eCRF. The Investigator will be required to electronically sign off on the clinical data when all the data is clean prior to database lock.

The monitor will review the eCRFs and evaluate them for completeness and consistency. The eCRF will be compared with the source documents to ensure that there are no discrepancies between critical data. The monitor cannot enter data in the eCRFs. All entries, corrections and alterations are to be made by the responsible Investigator or his/her designee. If additional corrections are needed, the responsible monitor or Data Manager will raise a query in the EDC application. The appropriate study center staff will answer queries sent to the Investigator. This will be audit trailed by the EDC application meaning that the name of investigational staff, time, and date stamp are captured.

The eCRF is essentially considered a data entry form and should not constitute the original (or source) medical records unless otherwise specified. Source documents are all documents used by the Investigator or hospital that relate to the subject's medical history, that verify the existence of the subject, the inclusion and exclusion criteria and all records covering the subject's participation in the study. They include but are not limited to laboratory notes, ECG results, memoranda, pharmacy dispensing records, subject files, etc. Source data should be attributable, legible, contemporaneous, original, accurate, and complete. Any changes to the source documents or cancellations should be signed and initialed with date. Changes to source data should be traceable, should not obscure the original entry, and should be explained if necessary (eg, via an audit trail).

The Investigator is responsible for maintaining source documents. These will be made available for inspection by the study monitor at each monitoring visit. The Investigator must submit a completed eCRF for each subject who is screened and enrolled in the study regardless of duration. All supportive documentation submitted with the eCRF, such as laboratory or hospital records, should be clearly identified with the study and subject number. Any personal information, including subject name, should be removed or rendered illegible to preserve individual confidentiality.

### User Roles and Responsibilities:

Once clinical data of the eCRF have been submitted to the central server, corrections to the data fields will be audit trailed, meaning that the reason for change, the name of the person who performed the change, together with time and date will be logged. Roles and rights of the study center staff responsible for entering the clinical data into the eCRF will be determined in advance.

Electronic CRF records will be automatically appended with the identification of the creator, by means of their unique User ID. Specified records will be electronically signed by the Investigator to document his/her review of the data and acknowledgement that the data are accurate. This will be facilitated by means of the Investigator's unique User ID and password; date and time stamps will be added automatically at time of electronic signature.

### Data Handling and Record Keeping

The Investigator must maintain essential study documents (protocol and protocol amendments, completed eCRFs, signed ICFs, relevant correspondence, and all other supporting documentation). The study center should plan on retaining such documents for approximately 15 years after study completion. The study center should retain such documents until at least 2 years after the last approval of a marketing application in an ICH region and until there are no pending or contemplated marketing applications in an ICH region or at least 2 years after the formal discontinuation of clinical development of the study treatment. These documents should be retained for a longer period if required by the applicable regulatory requirements or the hospital, institution, or private practice in which the study is being conducted. Subject identification codes (subject names and corresponding study numbers) will be retained for this same period of time. These documents may be transferred to another responsible party, acceptable to Sponsor, who agrees to abide by the retention policies. Written notification of transfer must be submitted to Sponsor. The Investigator must contact Sponsor prior to disposing of any study records.

### **Direct Access to Source Documents**

The Investigator will prepare and maintain adequate and accurate source documents to record all observations and other pertinent data for each subject randomized into the study.

The Investigator will allow Sponsor, [REDACTED] and authorized regulatory authorities to have direct access to all documents pertaining to the study, including individual subject medical records, as appropriate. Such information must be kept confidential and must have locked facilities that allow for this. Subject identification number will be recorded on all documents related to the study.

### **Study and Study Center Closure**

The Sponsor designee reserves the right to close the study center or terminate the study at any time for any reason at the sole discretion of the Sponsor. Study centers will be closed upon study completion. A study center is considered closed when all required documents and study supplies have been collected and a study center closure visit has been performed.

The Investigator may initiate study center closure at any time, provided there is reasonable cause and sufficient notice is given in advance of the intended termination.

Reasons for the early closure of a study center by the Sponsor or Investigator may include but are not limited to:

- Failure of the Investigator to comply with the protocol, the requirements of the IRB/IEC or local health authorities, the Sponsor's procedures, or GCP guidelines.
- Inadequate recruitment of subjects by the Investigator.
- Discontinuation of further study treatment development.

### **Publication Policy**

The data generated by this study are confidential information of the Sponsor. The Sponsor will make the results of the study publicly available. The publication policy with respect to the Investigator and study center will be set forth in the Clinical Trial Agreement.

[Redacted]

[Redacted]

[Redacted]

[Redacted]	[Redacted]	
[Redacted]	[Redacted]	[Redacted]
	[Redacted]	[Redacted]
	[Redacted]	[Redacted]
	[Redacted]	[Redacted]
	[Redacted]	[Redacted]
	[Redacted]	[Redacted]
	[Redacted]	[Redacted]
[Redacted]	[Redacted]	[Redacted]
	[Redacted]	[Redacted]
	[Redacted]	[Redacted]
	[Redacted]	[Redacted]
	[Redacted]	[Redacted]
	[Redacted]	[Redacted]

[REDACTED]	[REDACTED]	
	[REDACTED]	[REDACTED]
	[REDACTED]	[REDACTED]
	[REDACTED]	[REDACTED]
	[REDACTED]	[REDACTED]
	[REDACTED]	[REDACTED]
[REDACTED]	[REDACTED]	[REDACTED]
	[REDACTED]	[REDACTED]
	[REDACTED]	[REDACTED]
[REDACTED]	[REDACTED]	
[REDACTED]	[REDACTED]	
[REDACTED]	[REDACTED]	[REDACTED]
	[REDACTED]	[REDACTED]
[REDACTED]	[REDACTED]	[REDACTED]
	[REDACTED]	[REDACTED]
	[REDACTED]	[REDACTED]
	[REDACTED]	[REDACTED]
	[REDACTED]	[REDACTED]
	[REDACTED]	[REDACTED]
[REDACTED]	[REDACTED]	
	[REDACTED]	
	[REDACTED]	
[REDACTED]	[REDACTED]	
[REDACTED]	[REDACTED]	[REDACTED]
	[REDACTED]	[REDACTED]

[REDACTED]

[REDACTED]	[REDACTED]
[REDACTED]	

[REDACTED]

## APPENDIX 4: ADVERSE EVENTS: DEFINITIONS AND PROCEDURES FOR RECORDING, EVALUATING, FOLLOW-UP, AND REPORTING

### Definition of AE

AE Definition

 
• An AE is any untoward medical occurrence in a patient or subject, temporally associated with the use of study treatment, whether or not considered related to the study treatment.
 
• NOTE: An AE can therefore be any unfavorable and unintended sign (including an abnormal laboratory finding), symptom, or disease (new or exacerbated) temporally associated with the use of study treatment.
 

Events Meeting the AE Definition

 
• Any abnormal laboratory test results (hematology, clinical chemistry, or urinalysis) or other safety assessments (eg, ECG, radiological scans, vital signs measurements), including those that worsen from Baseline, considered clinically significant in the medical and scientific judgment of the Investigator (ie, not related to progression of underlying disease).
 
• Exacerbation of a chronic or intermittent pre-existing condition including either an increase in frequency and/or intensity of the condition.
 
• New conditions detected or diagnosed after study treatment administration even though it may have been present before the start of the study.
 
• Signs, symptoms, or the clinical sequelae of a suspected drug-drug interaction.
 
• Signs, symptoms, or the clinical sequelae of a suspected overdose of either study treatment or a concomitant medication. Overdose per se will not be reported as an AE/SAE unless it is an intentional overdose taken with possible suicidal/self-harming intent. Such overdoses should be reported regardless of sequelae.
 
• "Lack of efficacy" or "failure of expected pharmacological action" per se will not be reported as an AE or SAE. Such instances will be captured in the efficacy assessments. However, the signs, symptoms, and/or clinical sequelae resulting from lack of efficacy will be reported as AE or SAE if they fulfill the definition of an AE or SAE.
 

Events NOT Meeting the AE Definition

 
• Any clinically significant abnormal laboratory findings or other abnormal safety assessments which are associated with the underlying disease, unless judged by the Investigator to be more severe than expected for the subject’s condition.
 
• The disease/disorder being studied or expected progression, signs, or symptoms of the disease/disorder being studied, unless more severe than expected for the subject’s condition.
 
• Medical or surgical procedure (eg, endoscopy, appendectomy): the condition that leads to the procedure is the AE.
 
• Situations in which an untoward medical occurrence did not occur (social and/or convenience admission to a hospital).
 
• Anticipated day-to-day fluctuations of pre-existing disease(s) or condition(s) present or detected at the start of the study that do not worsen.
 
• Pregnancy itself is not regarded as an AE unless there is suspicion that the study treatment may have interfered with the effectiveness of a contraceptive medication. If a pregnancy is reported for a subject, no further study treatment will be administered to this subject and the outcome of all pregnancies (spontaneous miscarriage, elective termination, normal birth or congenital abnormality) must be followed up and documented. Follow-up should be performed up to delivery and examination of the newborn, after which a follow-up report should be sent with any new information regarding the pregnancy and the outcome of the birth.
 
• All congenital abnormalities/birth defects should be classified as SAEs. Spontaneous miscarriages should also be reported and handled as SAEs. Elective abortions without complications should not be handled as SAEs but should be reported as a follow-up report for the pregnancy. All outcomes of pregnancy must be reported to the Sponsor on a Pregnancy Outcomes Report Form.
 
• Pregnancy outcomes must be collected for the female partners of any males who took study treatment in this study. Consent to report information regarding these pregnancy outcomes should be obtained from the female partner.
 
• The pregnancy shall be followed every 3 months during pregnancy till its outcome and 1 month post-delivery. If there are abnormalities present at delivery, the newborn will be followed for an appropriate period, or up to 3 months, to assess the functional and health status of the child.
 
• Pregnancies must be reported to [REDACTED] using the reporting details provided in Section 8.3.4 within 24 hours of awareness.
 


**Definition of SAE**

If an event is not an AE per definition above, then it cannot be an SAE even if serious conditions are met (eg, hospitalization for signs/symptoms of the disease under study, death due to progression of disease).

An SAE is defined as, but is not limited to, an event that:

a) Results in death Death is not an AE in itself, but an outcome. The cause of the death is the AE which resulted in death.

b) Is life-threatening Life-threatening means that the subject was at immediate risk of death at the time of the SAE; it does not refer to an SAE that hypothetically might have caused death if it had been more severe. .

**c) Requires inpatient hospitalization or prolongation of existing hospitalization**

Hospitalization is defined as at least 1 overnight formal admission into hospital, usually in order to perform additional tests, provide treatment which it is not possible to provide at home and/or due to an unstable medical condition which requires specific monitoring of the subject. Pre-planned hospitalizations (known already prior to signing the ICF) for pre-existing condition, or a procedure required by the Clinical Investigation Plan, without a serious deterioration in health or if the hospitalization is clearly not associated with an AE (eg, social hospitalization) will not be considered an SAE, unless any of the above criteria are fulfilled over the course of the hospitalization due to unplanned complications. Any Hospitalization due to logistic reason will not be considered as SAE” “Social” hospitalization whereby it is administratively impossible to release the subject home is not necessarily an SAE. Complications that occur during hospitalizations are AEs unless they would qualify as an SAE for any of the above criteria. If the complication delays subject release from hospital, then the AE becomes an SAE. Hospitalizations which are not performed due to an AE are not regarded as SAEs.

**d) Results in persistent or significant disability/incapacity**

The term significant disability refers to any condition that impairs physical/physiological well-being to the extent that the subject is unable to function normally. Physical disability may include, but is not limited to, permanent disability of locomotion or motility, but also systemic permanent dysfunction including heart failure, liver insufficiency or pulmonary fibrosis.

**e) Is a congenital anomaly/birth defect****f) Is an important medical event:**

Important medical events that may not result in death, be life-threatening or require hospitalization may be considered as an SAE when, based on appropriate medical judgment, they may jeopardize the subject, or the subject may require medical or surgical intervention to prevent one of the outcomes listed in this definition.

## Recording and Follow-up of AE and/or SAE

### Definition of the Adverse Event Reporting Period

The AE/ SAE reporting period for safety surveillance begins after subject signs ICF. The safety surveillance continues until 20 weeks from last dose of study treatment administration. Any AE/-SAE occurred post 20 weeks from last dose of study treatment administration will be reported if it is considered related to study treatment by the Investigator.

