### 2.3 Benefit/Risk Assessment

Details about specific benefits and risks for subjects in this clinical study can be found in the IB and informed consent form (ICF).

Given that efficacy benefits were reported in the completed Phase 2b study [REDACTED] Phase 3 studies [REDACTED] in psoriasis, there is an expectation that subjects treated with tildrakizumab will demonstrate improvement in scalp psoriasis disease activity and quality of life.

The study has also been designed to minimize potential risks to subjects; all subjects will undergo screening procedures aimed at reducing the likelihood and impact of any such risks. In addition, regular safety monitoring during the treatment period for all subjects will ensure that any unanticipated effects of study participation are identified promptly and managed appropriately. In view of the long half-life ( $t_{1/2}$ ) of tildrakizumab at doses previously studied, subjects will continue to be monitored throughout [REDACTED] wash-out period following the end of treatment (EoT) visit, during which no active study treatment will be administered.

This study will be performed in compliance with the protocol, International Council for Harmonisation (ICH), Good Clinical Practice (GCP), and applicable regulatory requirements.

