#### **PART 3: Observational Safety Follow-up (Week 52 to Week 72)**

After Week 52 (or early termination of study treatment prior to Week 52), the study treatment should be stopped and all subjects, including those who terminated early from Part 1 and 2 will enter the [REDACTED] Observational Safety Follow-up Period to monitor safety and tolerability [REDACTED]  
[REDACTED] following last dose of study treatment. During the follow-up period, subjects should continue on study-approved concomitant medications only, however may be placed on appropriate

therapies for safety concerns or significant worsening of psoriasis based on the judgment of the Investigator. The subjects will not receive study treatment during the follow-up period.

[REDACTED]

[REDACTED]

[REDACTED]

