## 7.0 DISCONTINUATION OF STUDY TREATMENT AND SUBJECT DISCONTINUATION/WITHDRAWAL

### 7.1 Discontinuation of Study Treatment

Subjects may voluntarily discontinue study treatment for any reason at any time and enter the [REDACTED] wash-out period, or completely withdraw from the study [REDACTED]. Subjects who consent to enter the wash-out period will undergo the Week 52 (EoT) assessment a minimum of 4-weeks after administration of the last dose of study treatment.

At any time during Part 1 or Part 2 of the study, the Investigator should discontinue study treatment of a given subject if, on balance, he/she believes that continuation would be detrimental to the subject's well-being.

The study treatment must be discontinued under the following circumstances and the further steps need to be discussed with the Medical Monitor:

- An SAE, drug reaction or complication, or an unacceptable AE, whether attributed to study treatment or not, that precludes continuation of treatment with study treatment. This includes the development of allergic reactions or the development of other potentially serious drug reactions to medication required by the protocol
- Diagnosis of malignancy (except basal or squamous cell carcinoma of skin) during study (at discretion of the subject and Investigator)
- Subjects who develop suicidal behavior
- Evidence of pregnancy
- Withdrawal of informed consent
- Lost to follow-up
- Significant non-compliance of the subject with study procedures
- Decision of the Sponsor to terminate the subject, study center, or the study.

[REDACTED]

Subjects who withdraw from the study at any part will undergo the Week 52 (EoT) assessments. Patient related outcome (PRO) measurement should be obtained immediately after subject withdrawal. Week 52 (EoT) assessments should be conducted a minimum of 4-weeks after administration of the last dose of study treatment.

See the SoA [REDACTED] for data to be collected at the time of treatment discontinuation and follow-up and for any further evaluations that need to be completed.

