#### 8.3.1 Time Period and Frequency for Collecting AE and SAE Information

Any relevant observations made before the end of the Screening and Baseline visit (prior to first dose of study treatment) are to be recorded on the AE eCRF, but will not be considered TEAEs and will be reported separately from TEAEs. Any relevant observations made after the first dose of study treatment will be recorded as an AE in the subject's AE eCRF [REDACTED]

[REDACTED] For the purposes of this study, any detrimental change in the subject's condition, after the first dose of study treatment and up to completion of the EoS visit, should be considered

an AE. For those subjects who may withdraw during the Observational Safety Follow-up Period or wash-out period, at least 2 attempts should be made to collect the AEs.

A hospitalization planned by the subject prior to signing the ICF is considered a therapeutic intervention and not the result of a new SAE and should be recorded as medical history. If the planned hospitalization or procedure is executed as planned, the record in the subject's medical history is considered complete. However, if the event/condition worsens during the study, it must be reported as an AE.

Medical occurrences that begin before the start of study treatment but after obtaining informed consent will be recorded on the AE section of the eCRF, however will not be considered as TEAEs.

All SAEs will be recorded and reported to the CRO within 24 hours, as indicated in [Appendix 4](#). The Investigator will submit any updated SAE data to the CRO within 24 hours of it being available. The Investigator is responsible for informing the Ethics Committee of the SAE as per local requirements. All AEs/SAEs have to be reported to the Sponsor, whether or not considered causally related to the study treatment or to the study procedures.

Investigators are not obligated to actively seek AE or SAE after conclusion of the study participation. However, if the Investigator learns of any SAE, including a death, at any time after a subject has been discharged from the study, and he/she considers the event to be reasonably related to the study treatment or study participation, the Investigator must promptly notify the CRO.

The method of recording, evaluating, and assessing causality of AE and SAE and the procedures for completing and transmitting SAE reports are provided in [Appendix 4](#).

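### Protocol Appendix 4 and Section 8.3.1 set conflicting ends for all-cause AE/SAE reporting; a gap opens where a subject's EoS visit falls more than 20 weeks after the last dose

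*Protocol*

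**What the plan says.** Two parts of the protocol define when AE/SAE reporting ends.

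- **Appendix 4, Definition of the Adverse Event Reporting Period.** The window is tied to dosing: "The safety surveillance continues until 20 weeks from last dose of study treatment administration". Later AEs and SAEs are filtered by causality. An event that "occurred post 20 weeks from last dose of study treatment administration will be reported if it is considered related to study treatment by the Investigator" is in; any other is out.
- **Section 8.3.1.** The window is tied to a visit. Any worsening "after the first dose of study treatment and up to completion of the EoS visit" is an AE. There is no causality filter: "All AEs/SAEs have to be reported to the Sponsor, whether or not considered causally related to the study treatment or to the study procedures". This section has a related-only rule of its own, but it covers SAEs the Investigator learns of after the subject has left the study.

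The end of follow-up is also described in two ways.

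- The synopsis (Overall Design), Protocol Section 4.1 (Part 3) and SAP Section 3 (Part 3) count it from the last dose and place early terminators in it. The length is redacted, but the heading reads "PART 3: Observational Safety Follow-up (Week 52 to Week 72".
- Section 2.3 instead describes a "wash-out period following the end of treatment (EoT) visit, during which no active study treatment will be administered". For subjects who stop early, Section 7.1 adds: "Week 52 (EoT) assessments should be conducted a minimum of 4-weeks after administration of the last dose of study treatment".

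Section 8.3.6 lists malignancies, MACE and severe infections as AESIs, to be reported in the same way as SAEs, and states no time or causality limit there.

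**The concern.** The primary safety endpoints for malignancy, melanoma and non-melanoma skin cancer, MACE and severe infection are percentages of subjects with the event, whatever its cause. SAP Section 4.10.1 tabulates AEs, including these AESIs, for Part 1, for Parts 2 and 3, and overall. The visible TEAE definition has no end date. Events in follow-up therefore enter the tables if they are reported.

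A rule that keeps late events only when judged related works against an all-cause endpoint. Appendix 4 asks the Investigator to weigh alternative causes and timing. Events far from the last dose are thus natural candidates for the unlikely or unrelated categories, which SAP Section 4.10.1 groups as unrelated. An event never reported cannot be recovered at analysis; the SAP rule that treats missing causality as related does not help. Section 2.3 justifies follow-up by the drug's long half-life, so the period matters to the design.

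**Working it through.** **Inputs**
- Appendix 4 window: 20 weeks after the last dose.
- Part 3 length: Week 72 − Week 52 = 20 weeks, from the heading. Applying 20 weeks to early stoppers is an assumption, because the stated length is redacted.
- Scheduled Week 52 injection: SAP Section 3 (Part 2).
- Scheduled Week 44 injection: SAP Section 3 gives matching placebo to the tildrakizumab arm at Weeks 20, 32 and 44. Protocol Section 6.0 counts placebo as study treatment.
- EoT visit for early stoppers: at least 4 weeks after the last dose (Section 7.1).

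**Formula.** With last dose at week L, Appendix 4 ends all-cause reporting at L + 20. Section 8.3.1 ends it at the subject's EoS visit. Filtered weeks = max(0, EoS week − (L + 20)).

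**Results**

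| Case | EoS week | Appendix 4 end | Filtered weeks |
|---|---|---|---|
| Injected at Week 52, EoS at Week 72 | 72 | 52 + 20 = 72 | 0 |
| Early stopper, 20 weeks counted from last dose | L + 20 | L + 20 | 0 |
| Early stopper, 20 weeks counted from EoT visit | at least L + 4 + 20 = L + 24 | L + 20 | at least 4 |
| Last injected at Week 44, still followed to Week 72 | 72 | 44 + 20 = 64 | 72 − 64 = 8 |

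The first row reproduces the protocol's own alignment of 20 weeks with Week 72. The second and third rows differ only in which section's anchor is used. The fourth does not depend on that choice, but it needs a subject who misses the Week 52 injection and is not handled as an early termination.

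**Do other passages settle the conflict?** No. The AESI rule in Section 8.3.6 sends these events down the SAE route, but the Appendix 4 filter covers SAEs as well as AEs. Section 8.3.1 refers sites to Appendix 4 for SAE reporting and for recording methods, so a site has reason to follow the appendix. Section 4.4 defines EoS as the last visit of the last subject globally, so the visit meant in Section 8.3.1 is itself not pinned down for an individual.

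**The case against.** The strongest reply is that the design text ties follow-up to the last dose in three places: the synopsis, Protocol Section 4.1 and SAP Section 3. Only the benefit/risk narrative in Section 2.3 ties it to the EoT visit. With a 20-week follow-up from the last dose, the two windows close together and the Appendix 4 filter is simply the counterpart of the post-discharge rule in Section 8.3.1. Section 8.3.1 demands all events regardless of causality, and Section 8.3.6 places no limit on AESIs. For the Week 44 case, Section 6.4 asks for every effort to give a missed dose, and Weeks 64 to 72 lie beyond the 52-week primary safety objective in SAP Section 2.1. The follow-up length, the schedule of activities and part of Section 8.3.1 are redacted.

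Much of this stands, and it limits the consequence. A reader might infer that subjects who stop dosing early do lose unrelated-rated malignancies, MACE and infections from the primary safety endpoints. The documents do not establish that. It requires an EoS visit more than 20 weeks after the last dose, and the majority wording points to no gap. A reader might also picture early stoppers being followed to calendar Week 72, with 52 − L filtered weeks, but no visible text keeps them until then. Nor does any section give an interval from last dose to EoT longer than the 4-week minimum, so larger gaps cannot be documented.

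What does not stand is the view that nothing needs changing. The EoT anchor is in the protocol and contradicts the last-dose anchor. Interrupted and missed doses are foreseen (Sections 6.4, 6.6 and 7.1.1). SAP Section 4.10.1 tabulates Part 3 events despite the 52-week objective.

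**Conclusion.** The point holds as an internal contradiction with a conditional consequence. Appendix 4 and Section 8.3.1 give different ends and different causality rules for AE/SAE reporting, and no visible passage ranks them.

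The size is 0 weeks where dosing reaches Week 52 or a 20-week follow-up is counted from the last dose. It is at least 4 weeks if follow-up runs from the EoT visit, and 8 weeks for a subject last injected at Week 44 and followed to Week 72. Inside such a gap, events rated unrelated may be missing from all-cause percentages where a site applies Appendix 4.

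Confidence is high for the contradiction and moderate for the extent of loss. The extent rests on an assumed 20-week follow-up and on redacted text. The documents give no basis for estimating how many subjects or events would be affected. This should be corrected.

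**What to change.** Put one identical sentence in Section 8.3.1 and in Appendix 4: all AEs and SAEs, regardless of causality, are recorded and reported until the later of 20 weeks after the last dose and completion of the subject's own EoS visit; the related-only rule applies only once both have passed. State that the EoS visit here means that subject's last visit, not the global date in Section 4.4.

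Where the windows already coincide, this changes nothing; where they do not, it closes the gap whichever follow-up anchor applies. It needs no new visit or form. The cost is a few more unrelated AEs to record and report.
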